6. BENEFITS

There are no potential direct medical benefits for subjects participating in this research. Indirect benefits subjects may gain are a feeling of helping contribute to society, contributing to increased scientific knowledge, increased information about one's own health or knowledge of resources, improvement in psychological well-being due to interacting with research staff or content of interviews/questionnaires. Potential benefits this research has to society is the ability to quantify pain objectively in subjects undergoing labor pains. It will also help to improve our knowledge of pain processing in patients undergoing different types of neuraxial blocks.

7. PRIVACY AND CONFIDENTIALITY

All participant information and specimens are handled in compliance with the Health Insurance Portability and Accountability Act (HIPAA) and privacy policies of Stanford University, Stanford Health Care, and Stanford Children's Health.

Evaluation of Objective Pain Measurement Device

NCT03975660

October 24, 2024

Statistical Analysis Plan

The correlation coefficient will be calculated between patients' subjective pain ratings (NRS) and the calculated ROPA scores. Receiver operating characteristic (ROC) curves will be generated to evaluate the ability of the ROPA system to distinguish between clinically significant pain cut-off values representing no/mild, moderate, and severe pain, and area-under-the-curve (AUC) will be calculated. The comparisons performed during this analysis included the following clinically relevant cutoffs: no/mild pain (NRS \leq 3) vs. moderate-severe pain (NRS >3); no/mild/moderate pain (NRS \leq 6) vs. severe pain (NRS $>$ 6); and no/mild pain (NRS \leq 3) vs. severe pain (NRS $>$ 6). Prior to study initiation, performance thresholds were deemed to represent either good (70-79%), very good (80-89%) or excellent (> 90%) performance in terms of AUC. Finally, the correlation coefficient between the NRS and ROPA will be calculated.

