1. PURPOSE OF THE STUDY

a. Brief Summary

The aim of the study is to develop a device that can objectively measure pain. The study will attempt to objectively measure labor pain with an experimental device (CereVu ROPA). We will apply the device to determine if it is objectively able to measure patients reported pain due to uterine contractions before and after labor epidural analgesia. A brain oxygenation device, Edwards Foresight, will be used to concurrently monitor brain oxygenation and hemodynamics, so the relationship between the CereVu ROPA device objective measure of pain and brain oxygenation/hemodynamic changes and patient-reported pain can be determined.

b. Objectives

The investigators hope to learn: If the pain measurement device (CereVu ROPA) is capable of reflecting different levels of pain ratings in patients in labor having uterine contractions and then changes in pain after receiving different neuraxial techniques for labor pain. Additionally determine the relationship between the CereVu ROPA device, brain oxygenation/hemodynamic changes and patient-reported pain scores.

c. Rationale for Research in Humans

The pain measurement device is intended to be used in humans. The study is using dynamic psychophysical testing, which necessitates the use of specific pain-related questions in order to get patients' feedback.

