2. STUDY PROCEDURES

a. Procedures

This study contains two phases. In phase 1 (device algorithm development) and phase 2 (validating the device compared to your reported pain scores). Both phase will follow identical methods, only the data analysis is different. Qualified subjects will be identified and contacted by the anesthesia team prior to their clinical evaluation for labor neuraxial analgesia. Potential patients will be informed of the study, and if they choose to participate, all to investigate be answered and an informed consent form will be signed prior to any study related activities. When they request labor analgesia, the area where the sensors of the pain measurement devices (CereVu ROPA and Edwards Foresight) will be applied to will be prepped with an alcohol swab. After allowing to dry, the sensors will be applied to the forehead on each side of the head and connected to the devices. Data recording is then started. CereVu ROPA: Patients brain activity "objective pain" data

will be obtained by the sensor and will be stored on a custom-built, radio shielded device that stores the data for further offline analysis along with patient-reported pain measures. Edwards Foresight device: Will be used to concurrently to monitor brain oxygenation and hemodynamics, so the relationship between the CereVu ROPA device objective measure of pain and brain oxygenation/hemodynamic changes and patient-reported pain can be determined. After collection of baseline data for device algorithm development of up to 70 patients, we will be moving to clinical validation study in which patients will receive our institution's standard labor epidural based on clinician preference (either epidural, dural puncture epidural or combined spinal epidural) to provide labor analgesia. Patients will undergo their standard medical and obstetric treatment at the discretion of the obstetrical and anesthesia team. There will be no delay in their treatment due to this study, and the device data will not be available of influence care. During the time of preparation of block, we will be obtaining baseline data. The research staff will be recording pain scores with contractions at regular intervals until approximately 45 minutes after the epidural is placed and the patient is comfortable.

b. Procedure Risks

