4. PARTICIPANT POPULATION

a. Planned Enrollment

This study will be done in two phases.

- i) In the validation study, 70 patients in labor will be recruited to get the baseline data.
- ii) Then in the clinical trial, we will be enrolling 60 patients to determine how the objective pain devices measurements correspond with the patient's reported pain score before and after labor epidural analgesia. The study population will be representative of the general laboring patient population receiving epidural analgesia (epidural, combined-spinal epidural and dural puncture epidural as per clinician preference).

b. Age, Gender, and Ethnic Background

All ethnicities will be included. All females from 18 to 50 years will be included in the study.

c. Vulnerable Populations

The study will involve 130 pregnant women. Patients will be connected to the pain measurement devices via a sensor that will be applied to their forehead on each side. This carries a minimal risk of skin irritation. Patients will be monitored closely in the hospital per routine labor pain management. Analgesia will be provided by the obstetric anesthesia team per hospital routine, using all of the guidelines required to minimize risk. Every effort will be made to make sure subjects are comfortable while they complete the questionnaires.

d. Rationale for Exclusion of Certain Populations

Minors will not be included in this study.

e. Stanford Populations

These groups will not be targeted. If anyone from these groups will participate, they will be subject to the same inclusion/exclusion criteria, and provide the same written informed consent.

f. Healthy Volunteers

NA

g. Recruitment Details

In the LPCH labor and delivery, research personnel will first identify the patients suitable for the study by chart review and then they will be given information leaflets for the study. Research personnel will conduct all discussions about the study and answer any questions in a private manner.

h. Eligibility Criteria

i. Inclusion Criteria

1. Age 18-50

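### A single NRS-ROPA correlation and three AUCs without intervals cannot by themselves show that ROPA follows a woman's own pain, or place an AUC securely in a performance band

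*SAP*

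**What the plan says.** The SAP is one paragraph. It plans a correlation between "subjective pain ratings (NRS) and the calculated ROPA scores" and repeats this at the end: "Finally, the correlation coefficient between the NRS and ROPA will be calculated". It also plans ROC curves and AUCs for three contrasts: NRS ≤3 against >3, ≤6 against >6, and ≤3 against >6. For the AUCs, "performance thresholds were deemed to represent either good (70-79%), very good (80-89%) or excellent", the last meaning above 90%. No unit of analysis, clustering method, standard error or confidence interval is named.

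The protocol, section 2a, has research staff "recording pain scores with contractions at regular intervals until approximately 45 minutes after the epidural is placed", so several scores per woman are part of the design. Section 1b asks whether the device reflects different levels of pain and "then changes in pain after receiving different neuraxial techniques for labor pain". Section 4a(ii) sets the comparison with reported pain before and after the epidural in the second phase: "in the clinical trial, we will be enrolling 60 patients". No statistical section in the protocol fills the gap.

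**The concern.** Two things are at stake.

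- **What the coefficient measures.** Whether ROPA moves when a woman's own pain moves is a within-woman question. An overall coefficient over pooled scores also reflects how far women's ROPA levels sit apart for reasons unrelated to pain. A weak tracker with a common baseline and a strong tracker whose baseline varies between women can give the same planned output. They call for different conclusions about the device.
- **How secure a label is.** An AUC is to be called good, very good or excellent according to a band about 0.10 wide. Without an interval that respects repeated scores, the reader cannot tell whether the AUC lies well inside its band or could equally belong to the next one.

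**Working it through.** The plan gives no precision target or expected value to reproduce, so the check is a model with stated assumptions.

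**Inputs from the documents.** Protocol 4m gives about 15 minutes before and 45 minutes after placement, 60 minutes in all. Protocol 4h requires contractions at least every 5 minutes. Scoring every 5 minutes would give 60/5 = 12 scores. The scoring interval is not stated, so 12 is an assumption. Section 4a(ii) gives 60 women.

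**Assumed pain course.** Three scores before the epidural (mean NRS 7) and nine after it (mean 7·exp(−t/10), t = 5 to 45 minutes); residual SD 1; between-woman NRS SD 0, 1 or 2; NRS rounded and limited to 0–10. The NRS ICC in this model is −0.08 to 0.18. ROPA = NRS + noise + a fixed offset per woman. The noise sets the within-woman correlation r_w. The offset SD is k times the within-woman ROPA SD.

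**Step 1: overall correlation.** With NRS ICC near zero and offsets unrelated to pain, the offset inflates ROPA variance by the factor 1 + k² and leaves the covariance unchanged:

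r_overall ≈ r_w / √(1 + k²)

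| r_w | k | Formula | Simulated, NRS SD 1 |
|---|---|---|---|
| 0.35 | 0 | 0.35/√1 = 0.35 | 0.35–0.36 in all three rows |
| 0.50 | 1 | 0.50/√2 = 0.354 | |
| 0.80 | 2 | 0.80/√5 = 0.358 | |

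The simulated values are large-sample ones (30,000 women, 12 scores each). The three AUCs were about 0.69, 0.71 and 0.74 in every row. The match also holds at NRS SD 0 (r 0.34) and SD 2 (r 0.38–0.39). The planned outputs therefore cannot tell these three devices apart.

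**Step 2: direction and size.** The factor 1/√(1 + k²) is at most 1, so offsets pull the overall coefficient below r_w. At k = 0.5 and r_w = 0.80 the formula gives 0.80/√1.25 = 0.716, a loss of 0.084. At k = 2 it gives 0.358, a loss of 0.442. In simulation the overall r stayed within 0.10 of r_w for k of 0 to 0.5, and was 0.08 to 0.46 lower for k of 1 to 2.

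**Step 3: can a non-tracking device pass?** Take a device that knows each woman's mean NRS exactly and follows nothing within her. At NRS SD 0 to 1 it reaches r of at most 0.29 and AUCs of at most 0.67, below the lowest band. At NRS SD 2 it reaches r 0.50 and AUCs of 0.70, 0.75 and 0.79.

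**Step 4: interval width.** Resampling women, with 60 women × 12 scores, r_w = 0.7 and NRS SD 1, AUC 95% intervals were 0.04–0.05 wide at k = 0, 0.07–0.09 at k = 1 and 0.08–0.10 at k = 2. Repeat runs put the range at about 0.04 to 0.11, and a wider grid of NRS SD and r_w gave 0.03 to 0.13. For an AUC of 0.75, mid-band, a width of 0.04 gives 0.73–0.77, inside the good band. A width of 0.11 gives 0.695–0.805, which covers the whole band and both its edges.

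**The case against.** The strongest reply is that the harm depends on something the documents never show. Nothing says that ROPA has large between-woman offsets, and with small ones the overall and within-woman coefficients nearly agree. The device is also judged on absolute NRS cutoffs, so an overall coefficient and overall AUCs are legitimate summaries. The plan contains no hypothesis test, and device data do not influence care. All of this stands. It limits the size of the point but does not supply the missing interval or isolate within-woman change.

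Three stronger readings are tempting and not supported.

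- *The device will look better than it is.* In the model, offsets make it look worse. False credit to a non-tracker reaches the good band only at the largest assumed NRS spread.
- *The intervals will be too narrow.* The SAP plans no interval at all, so there is no independent-observations interval to criticise. Had one been used, its error could go either way: the ratio of true to naive AUC standard error was 0.80 to 1.47 with 60 × 12 scores.
- *The population analysed is unknown.* The SAP names no phase, and section 2a says "Both phase will follow identical methods, only the data analysis is different". But that section makes phase 2 the validation against reported pain, and section 4a(ii) gives that comparison to the 60 women. What remains is a labelling slip: section 4a(i) uses the term validation study for the phase in which "70 patients in labor will be recruited to get the baseline data".

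The added coefficient has a limit of its own. Over an epidural course it is driven largely by the shared fall in pain, so any signal that shifts with time or with the block would score well. It does not by itself prove tracking from contraction to contraction.

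**Conclusion.** The point holds as a cheap improvement. The SAP names no unit, no method for repeated scores and no interval, and the protocol does not supply them. If the scores are pooled, the single coefficient cannot by itself answer the question about change in a woman's own pain, and an AUC alone cannot be placed securely in a band.

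The size cannot be fixed from the documents. It rests on the assumed pain course, 12 scores per woman and the assumed ROPA offsets. Under those assumptions the masking is material at offsets of 1 to 2 times the within-woman ROPA SD and small at 0 to 0.5. The interval can be anything from under half a band to slightly more than a whole one. The point does not show that the planned correlation or AUCs are invalid.

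**What to change.** Keep the overall correlation and the three AUCs, and add the following to the SAP:

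1. State the unit of analysis, the scoring interval and, in one line, the phase analysed.
2. Add a within-woman (repeated-measures) correlation, or a mixed model of NRS with ROPA split into the woman's mean and her deviation from it. State that the within-woman result largely reflects the common fall in pain after the epidural.
3. Give the correlations and each AUC a 95% confidence interval from a bootstrap that resamples women, and read the performance bands alongside those intervals.

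The cost is SAP wording and a short script, with no new data and no change to care. The downsides are slightly more analysis, intervals that may cross a band, and a percentile bootstrap that is only approximate: nominal 95% intervals covered 90 to 96% in the simulations.

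### Does the SAP leave open which women validate the device, given that section 4a attaches the validation label to the 70 development women?

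*SAP*

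**What the plan says.** Protocol section 2a names the phases: "In phase 1 (device algorithm development) and phase 2 (validating the device compared to your reported pain scores". It then says "Both phase will follow identical methods, only the data analysis is different", and gives the order and size of the first phase: "After collection of baseline data for device algorithm development of up to 70 patients, we will be moving to clinical validation study".

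Section 4a(i) describes the first set in other words: "In the validation study, 70 patients in labor will be recruited to get the baseline data". Section 4a(ii) describes the second: "we will be enrolling 60 patients to determine how the objective pain devices measurements correspond with" the women's own pain scores before and after the epidural. Section 4c gives the total: "The study will involve 130 pregnant women".

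The SAP plans a correlation between "subjective pain ratings (NRS) and the calculated ROPA scores", and ROC curves with AUC for three contrasts of NRS category. It grades AUC as good (70-79%), very good (80-89%) or excellent (above 90%). It names no phase, analysis set or number of women.

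**The concern.** If the analysis is the only thing that separates the phases, the SAP is where a reader expects to see two analyses, or at least a statement of which women the single analysis covers. It has neither. Nor does either document describe how the ROPA score is built, or say that it is fixed before the second phase starts. The one sentence that puts a number next to the word validation then points to the 70 women whose data develop the algorithm.

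What is at stake is the meaning of the graded AUC. A score fitted to a set of women discriminates better in those women than in new ones. If the 70 were graded alone, or pooled with the 60, a result could move up a band through overfitting. Because procedures are the same in both phases, all 130 women would have the data needed for such an analysis.

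**Working it through.** **1. The count.** Inputs: 70 and 60 (section 4a), total 130 (section 4c). 70 + 60 = 130, so the stated total is reproduced. The sets are distinct and together make up the whole study. The mismatch is in a label, not in the numbers.

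**2. The sets side by side.**

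| | Section 2a | Section 4a |
|---|---|---|
| First set | up to 70 women; baseline data; algorithm development | 70 women; baseline data; labelled validation |
| Second set | follows the first; compared with reported pain; labelled validation | 60 women, introduced as coming next; device measurements against reported pain |

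Order, size and purpose agree in both rows. Only the label in 4a(i) is out of place, and its own sentence gives the purpose as baseline data, which is what section 2a collects for development.

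**3. Where the SAP analysis belongs.** The SAP compares ROPA with NRS. Section 2a defines phase 2 as that comparison, and section 4a(ii) assigns it to the 60. No sentence assigns it to the 70 or to all 130. The score also has to exist before it can be validated, and section 2a moves to validation after the development data are collected.

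**4. Two side points.** A ceiling of 70 in section 2a and a planned 70 in section 4a do not conflict, and the 60 in 4a(ii) is not conditional on phase 1. The objective in section 1b, whether the device "is capable of reflecting different levels of pain ratings in patients in labor having uterine contractions", names no phase, but an objective need not.

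**5. What a misreading would do.** This needs inputs that the documents do not give, so it is illustration only.

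*Precision.* Assume AUC *A* = 0.80, one rating per woman and *m* women in each of two equal classes. Hanley-McNeil gives

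var = [*A*(1 − *A*) + (*m* − 1)(*P*₁ − *A*²) + (*m* − 1)(*P*₂ − *A*²)] / *m*², with *P*₁ = *A*/(2 − *A*) = 0.6667 and *P*₂ = 2*A*²/(1 + *A*) = 0.7111.

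For 60 women (*m* = 30): [0.16 + 29 × 0.0267 + 29 × 0.0711]/900 = 0.00333, SE 0.0577, 95% half-width 1.96 × 0.0577 = 0.113. The same formula gives 0.105 for 70 women and 0.076 for 130.

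*Optimism.* If all 130 were scored, 70/130 = 54% would be development women. A simulation fitted a least-squares score on 70 women and compared its AUC in all 130 with its AUC in 60 new women. It assumed 5, 20 or 40 features (one informative, with AUC 0.60 to 0.90), 2, 6 or 12 ratings per woman, feature ICC 0.3 or 0.7, outcome ICC 0, 0.3 or 0.7, and 50% prevalence: 378 settings, 150 runs each.

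| Features | Pooled minus new 60, median (range) |
|---|---|
| 5 | 0.01 (0.002 to 0.05) |
| 20 | 0.05 (0.01 to 0.12) |
| 40 | 0.08 (0.02 to 0.18) |

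The overall range is 0.002 to 0.178. With the informative feature at mid-band, pooling raised the grade in a median 5% of runs with 5 features (range 0 to 30%) and 52% with 40 (0 to 96%). The answer is set almost entirely by the assumed feature count, ratings per woman and ICCs.

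**The case for a change.** The strongest case for a change is that the intent has to be inferred, against a contrary label, in a study that grades its own performance. Nothing in the SAP's wording excludes the 70. Neither document says that the score is frozen before phase 2. With a flexible score the difference could be a whole band, and a reader cannot tell whether the score is flexible. The remedy would cost a few sentences.

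Part of this stands. The label in 4a(i) is wrong when set against section 2a, and the SAP is silent on its analysis set. Both are real gaps in the writing.

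The step from there to a flawed result does not stand. It needs an analyst to set aside the stated purpose of phase 2 and of the 60 women, and to run an analysis that no sentence proposes. The simulation cannot supply the missing link: it shows that pooling would matter under some assumptions, not that pooling is planned. Nor would a rule that the score be built on phase 1 data alone be justified. Independent validation requires only that the 60 women's data play no part in building the score; other earlier data could be used without harm. Finally, parts of the SAP are in the past tense. If the analysis is already done, new planning text would alter nothing, and the report will have to state how many women were analysed in any case.

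**Conclusion.** The concern does not call for a change to the plan. It consists of a clerical slip in section 4a(i) and a missing detail in the SAP that the protocol supplies. Read together, sections 2a and 4a(ii) direct the correlations and graded AUCs to the 60 phase 2 women, and carrying that out gives a sound validation estimate. Naming the set in the SAP would leave the analysis as it is, so the effect on the result is nil.

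This rests on two assumptions: that the analysts follow the protocol's division of the phases, and that the 60 women's data are not used to build the score, which is what separating development from validation means. The documents imply both and contradict neither. The illustrative gain of 0.002 to 0.178 in AUC would apply only if the first assumption failed and all 130 women were scored. The report's stated number of women, 60 or 130, would show whether that had happened.

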2. ASA I-III +/-E
3. Patient requesting epidural labor analgesia
4. Good toco tracing (clearly showing contractions at least every 5 minutes)
5. Pain score greater than or equal to 3 out of 10 with contractions

ii. Exclusion Criteria

1. History of chronic pain
2. History of chronic opioid use
3. BMI > 45
4. Allergy to sensor adhesive material, local anesthetic or opioids
5. Contraindication to neuraxial block
6. Patient on magnesium infusion
7. Inability to give informed consent
8. Severe co-morbidities

i. Screening Procedures

Prospective subjects will be asked if they want to participate in this research study. If their answer is yes this will be documented on a Screening Questionnaire and they will be considered eligible to participate. Informed consent will then be obtained.

j. Participation in Multiple Protocols

Subjects will be asked if they are currently participating in other studies. If they are, each case will be evaluated separately to determine the potential for harm to subjects, or confounding study data. If it is determined that participating in more than one study at a time compromises either subject health or viability of the study data, subjects will not be enrolled.

k. Payments to Participants

There will be no payment for patients participating in this study.

l. Costs to Participants

There will be no charge to study subjects.

m. Planned Duration of the Study

The study is anticipated to take 1-1.5 years.

The total time per participant will likely be:

- i) Patients requesting labor epidural will be screened. If interested, the study is described in more detail to them and written informed consent will be obtained. This screening process will take 10 minutes.
- ii) The period of active participation will be approximately 1 hour to obtain baseline data while setting up for the epidural (15 minutes), and then measure pain for 45 min after epidural placement.
- iii) Individual data analysis will take approximately 4 weeks.

5. RISKS**a. Potential Risks****i. Investigational devices**

Patients will be connected to two objective pain measurement devices (CereVu ROPA and Edwards Foresight) via a sensor that will be applied to their forehead (one sensor on each side of their forehead).

ii. Investigational drugs

NA

iii. Commercially available drugs, biologics, reagents or chemicals

NA

iv. Procedures

Non-investigational procedures include:

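### Every woman is scored before and then after the block, and the SAP's AUCs and correlation carry no period, time or within-patient term, so an AUC in the good band does not by itself show that ROPA follows pain level

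*SAP*

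**What the plan says.** **Aims.** Protocol section 1b wants to learn whether the device succeeds in "reflecting different levels of pain ratings in patients in labor having uterine contractions and then changes in pain after receiving different neuraxial techniques". That covers both level of pain and change after the block. Section 4a describes the 60-woman phase as one to "determine how the objective pain devices measurements correspond with the patient's reported pain score before and after labor epidural analgesia".

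**Order of readings.** Section 4h admits women with a "Pain score greater than or equal to 3 out of 10 with contractions". Section 4m plans about an hour of participation, to "obtain baseline data while setting up for the epidural (15 minutes), and then measure pain for 45 min after epidural placement". Under section 2a, staff keep "recording pain scores with contractions at regular intervals until approximately 45 minutes after the epidural is placed and the patient is comfortable". All women in this phase receive a neuraxial block, and the sequence is the same for each of them.

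**Analysis.** The SAP plans one NRS-ROPA correlation, and ROC curves meant to show whether ROPA can "distinguish between clinically significant pain cut-off values representing no/mild, moderate, and severe pain". There are three contrasts: NRS >3 vs ≤3, >6 vs ≤6, and >6 vs ≤3. For AUC it says that "performance thresholds were deemed to represent either good (70-79%), very good (80-89%) or excellent", the last meaning above 90%. It names no period, time or patient term and does not say how repeated readings from one woman enter.

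**The concern.** Readings before the block should lie mostly in the higher pain classes and later readings mostly in the lower ones. Anything in the signal that changes at the block, or drifts over the hour, will then separate the SAP's pain classes even if it carries no information about pain. The documents leave such a route open: section 1a has a second monitor running so that the "relationship between the CereVu ROPA device objective measure of pain and brain oxygenation/hemodynamic changes and patient-reported pain can be determined", which treats the link with hemodynamics as an open question.

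At stake is what the performance label can support. An AUC called good or very good could be read as evidence that ROPA grades pain, when the planned analysis cannot tell grading from a response to the block or to elapsed time.

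**Working it through.** The documents give no AUC target calculation, NRS distribution, onset speed, reading count or device shift, so there is no stated figure to reproduce. The fixed order, entry rule, contrasts, bands and 60 women come from the documents. Everything else below is an assumption.

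**1. Closed form for a pain-blind signal.** Let the signal shift by d SD at the block and carry no pain information within a period. Let b1 and b0 be the shares of higher-pain and lower-pain readings that were taken before the block. Then

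AUC = 0.5 + (b1 − b0) × [Φ(d/√2) − 0.5].

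A perfect before/after flag has AUC F = 0.5 + (b1 − b0)/2, so b1 − b0 = 2F − 1.

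**2. Central setting.** Assume NRS readings at −15, −10 and −5 minutes and every 5 minutes from 5 to 45. Pre-block mean is 7, with exponential fall to 0 (time constant 10 minutes), between-woman SD 1.5 and within-woman SD 1.0. The simulated flag AUCs are 0.87, 0.93 and 0.98, so 2F − 1 = 0.74, 0.86 and 0.96. Φ(d/√2) is 0.638, 0.760 and 0.856 at d = 0.5, 1.0 and 1.5.

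| Shift at block | >3 vs ≤3 | >6 vs ≤6 | >6 vs ≤3 |
|---|---|---|---|
| 0.5 SD | 0.5 + 0.74×0.138 = 0.60 | 0.62 | 0.63 |
| 1.0 SD | 0.5 + 0.74×0.260 = 0.69 | 0.72 | 0.75 |
| 1.5 SD | 0.5 + 0.74×0.356 = 0.76 | 0.81 | 0.84 |

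**3. Range over 48 assumed settings** (pre-block mean 5-8; constant 5, 10 or 20 minutes; between-woman SD 1 or 2; within-woman SD 0.8 or 1.5).
- 0.5 SD: 0.56-0.64; never 0.70.
- 1.0 SD: 0.62-0.76; at least 0.70 in 19, 33 and 45 of 48 settings by contrast.
- 1.5 SD: 0.67-0.86; at least 0.70 in 37, 48 and 48 of 48. Above 0.90 is never reached.
- If NRS settles at 1 instead of 0, the lower ends become 0.55, 0.60 and 0.64.
- With one reading before and one after per woman, the ranges are 0.57-0.65, 0.64-0.76 and 0.68-0.86, so summarising per woman does not remove the effect.

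An independent rerun agreed with these ranges to about 0.01 and with the counts to within two settings.

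**4. Trials of 60 women at 1.0 SD.** In the central setting at least one AUC reaches 0.70 in about 97-98% of trials, but all three do in only about 35-36%. With a slower fall (constant 20) the figures are about 80% and 0.3%. At 0.5 SD at least one AUC reaches 0.70 in 0-3% of trials.

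**5. Time drift alone, central setting.** A drift of 1 SD over the hour gives about 0.65/0.63/0.66 (0.63-0.67 across runs), below every band. A drift of 1.5 SD gives 0.71/0.69/0.73.

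**6. Three different signals, similar AUCs** (sizes chosen, not estimated).
- Block-only at 1.5 SD: 0.76/0.81/0.84.
- Time-only at 2.5 SD over the hour: 0.81/0.79/0.84.
- True pain tracking at 0.2 SD per NRS point: 0.77/0.80/0.84.

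**7. Does an added analysis separate them?**
- A model of NRS on ROPA with patient and time-point effects and patient-clustered SEs is significant in 4-7% of trials for the first two signals and in at least 99.8% for the third.
- The pre-block AUC (>6 vs ≤6) averages 0.65-0.66 for the true pain signal. It is below 0.70 in 83-87% of trials, yet distinguishable from 0.50 in about 95%.
- The model is not decisive. A signal that follows each woman's own block onset passes it in 6-56% of trials, while its pre-block AUC stays at 0.50.

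**The case against.** **The before/after contrast is itself an aim.** Sections 1b and 4a ask for it, and the SAP claims only discrimination at NRS cut-offs. This stands: the combined AUCs are legitimate for that aim and should be kept. But section 1b also asks about levels of pain with contractions, and the SAP has nothing that isolates this.

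**The size rests on a shift nobody has measured.** This also stands. At 0.5 SD the problem does not reach the bands at all. It also weakens if pain class follows period loosely. With NRS >3 in 80% of readings before and 30% after, and three readings after for each one before, b1 − b0 = 0.384. No block-only signal can then exceed 0.5 + 0.384/2 = 0.69. Leaving the oxygenation relationship to be determined is not evidence that a non-pain shift exists.

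**The second monitor is a safeguard.** It is a partial one in the protocol, but the SAP contains no analysis of it.

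**Stronger readings that do not hold.** A reader might infer that a 1 SD movement of any origin earns the label. That is wrong for a time drift, which needs about 1.5 SD, and at 1 SD a block shift reaches only the lowest band. A reader might also take the added model as proof of pain tracking. The own-onset result in step 7 rules that out, so the model is supportive evidence only.

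**Conclusion.** The point holds in a limited form. The fixed order and the absence of a period, time or within-patient term are plain in the documents. It follows that reaching the good band is not sufficient evidence that ROPA reflects pain level, as distinct from change after the block. With a block-only shift of 1.0 SD the label can be good, and at 1.5 SD up to very good. Excellent is not reached at any shift examined across the 48 settings.

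These sizes depend on assumed NRS distributions, reading schedules and device shifts. A reader might conclude that ROPA does not measure pain or that the planned AUCs are invalid. The documents support neither: they give no non-pain shift, and the combined AUC answers a stated aim. The matter should be fixed, with medium confidence in how much it would change the reading of the results.

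**What to change.** - Keep the three combined AUCs and the correlation, state how repeated readings enter, and label the results as including the epidural effect.
- Print the AUC of a before/after indicator beside them as context. It is not a pass mark: the true pain signal in step 6 scores below the flag's 0.87/0.93/0.98.
- Add, as supportive evidence of pain tracking, one within-patient model of NRS on ROPA with patient effects, time relative to block (for example 5-minute bins) and patient-clustered SEs.
- Read it together with one pre-block AUC for NRS >6 vs ≤6, with a patient-clustered interval, judged against 0.50. State that the 70/80/90% bands do not apply to it, because the pain range is restricted before the block. Pre-block contrasts using NRS ≤3 are too sparse: about 4 of 180 readings (60 women × 3) at mean 7.
- State the limits. A signal following each woman's own onset can pass the model. The pre-block AUC mainly compares women; a 1 SD device offset between women cuts it to about 0.61. A null result does not prove absence of tracking: at 0.1 SD per NRS point the model detects 78-79% and the pre-block AUC 45-48%.

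**Cost.** A cheap improvement: a little more analysis, and no new data beyond each score's time relative to placement, which staff already have to follow in order to stop at about 45 minutes. The added measures are less precise: the pre-block AUC has an SE of about 0.04-0.05 in 60 women, against about 0.02-0.03 for the combined AUCs.
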